7 DATA MONITORING COMMITTEE AND OTHER EXTERNAL COMMITTEES

An independent data monitoring committee (DMC) will be constituted for review of safety information and assessment of overall benefit/risk balance in this study. Specific data to be reviewed and timing of the reviews by the DMC will be described in a DMC Charter.

8 STATISTICAL CONSIDERATIONS

8.1 Sample Size Determination

The size of the study is not based on testing a formal statistical hypothesis. The Escalation Cohort is a Phase 1 safety phase and the sample size cannot be precisely determined and depends on the observed toxicities; it is estimated that a total of 6 subjects will be treated in this cohort, assuming 600 mg and 800 mg are explored. For the Expansion Cohort (Phase 2), a sample size of 40 subjects per treatment group will allow estimation of the response rate with the following degree of precision, where response is defined by complete remission ($CR/CR_i = CR + CR_i$). A response rate of 0.6 will be estimated with the following 95% exact confidence interval (CI): 0.43 - 0.75. If the response rate is 0.45, then the associated 95% CI will be 0.29 - 0.62.

8.2 Populations for Analyses

The following populations will be defined for each cohort.

- *All Enrolled Subjects*: All subjects who signed an informed consent form. Subject disposition will be tabulated using this dataset.
- *All Randomized Subjects* (Expansion Cohort only): All subjects who signed an informed consent form and were randomized to either ulocuplumab 800 mg or 1000 mg in combination with LDAC or to LDAC alone. This dataset will be used for baseline and efficacy analyses.
- *All Treated Subjects*: All subjects who received at least one dose of study medication (ulocuplumab in the combination arm and LDAC in the LDAC only arm). This dataset will be used for safety analyses (as well as some efficacy analyses).
- *PK Subjects*: All treated subjects who received at least one dose of ulocuplumab and have evaluable PK data.
- *Immunogenicity Subjects*: All subjects treated with ulocuplumab who have baseline and at least one post baseline immunogenicity assessment.

8.3 Endpoints

8.3.1 Primary Endpoint(s)

- Phase 1 (escalation cohort): DLTs in Cycle 1, and AEs, \geq Grade 3 AEs, AEs leading to discontinuation, SAEs, deaths and laboratory abnormalities in combination therapy during the Treatment period plus 30 days of follow-up will be the primary endpoints for this study. AEs will be graded according to NCI CTCAE v4.03
- Phase 2 (expansion cohort): Investigator will assess best overall response. The primary endpoint will be based on the rate of Complete Remission (CR/CRi) prior to the initiation of any alternative therapy (including any subsequent ulocuplumab 800 mg for subjects in the LDAC alone arm). The primary analysis will be conducted after all patients had an opportunity for 6 months of follow-up. Please refer to [Appendix 1](#) for AML response criteria.

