APPENDIX 1 2003 IWG RESPONSE CRITERIA FOR AML

Table 1: 2003 IWG Response Criteria for AML

Response	Definition	Criteria
CR	Morphologic leukemia-free state	Bone Marrow: < 5% blasts with normal maturation of cell lines. Peripheral blood: - Absolute neutrophil count > 1000/ μ L - Platelets \geq 100,000/ μ L - Blasts 0% No residual evidence of extramedullary disease. Independent of RBC transfusions. No Auer rods present in bone marrow blasts.
CRi	Morphologic leukemia –free state with incomplete blood count recovery	Same criteria as CR except: platelet count < 100,000/ μ L and/or absolute neutrophil count < 1000/ μ L
PR	Regression of leukemia	\geq 50% decrease (from baseline) in the percentage of blasts to 5% to 25% in the bone marrow aspirate and all the hematologic values for CR. Bone marrow blasts <5% but with Auer rods present.
Treatment Failure (TF)	Failing to achieve a complete or partial remission	Failure to achieve a CR, CRi, or PR during the treatment period. Last posttreatment peripheral blood smear and/or bone marrow aspirate/biopsy show persistent leukemia.
Relapse (after CR/CRi)	Morphologic recurrence of leukemia	Reappearance of leukemic blasts in the peripheral blood or \geq 5% blasts in the bone marrow not attributed to any other cause. Reappearance or development of cytologically proven extramedullary disease.
PD (after PR)	Morphologic increase in leukemia	50% increase (from nadir) in either leukemia peripheral blood involvement (absolute count), bone marrow leukemia infiltrate, or extramedullary site of disease, if applicable.

Abbreviations: CR = complete remission; CRi = complete remission with incomplete blood count recovery; PR = partial remission; PD = progressive disease; RBC = red blood cells.

Source: Cheson BD, Bennett JM, Kopecky KJ et al. Revised Recommendations of the International Working Group for diagnosis, Standardization of Response Criteria, Treatment Outcomes, and Reporting Standards for Therapeutic Trials in Acute Myeloid Leukemia. J Clin Oncol 2003; 21: 4642-4649.

Leukemia responses will be assessed after each cycle as follows: CR, CRi, PR, TF, PD, or Relapse as described above. Local laboratory reports supporting assessments will be sent to BMS. Subjects without local laboratory reports will be recorded as not done.

APPENDIX 2 SIMULATION TO EXAMINE MTPI VS. TRADITIONAL 3+3 DESIGN FOR DOSE ESCALATION STUDY WITH 2 DOSE LEVELS

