2.2 Study Design

A total number of 6 (Phase 1) plus up to approximately 120 (Phase 2), i.e. 126 subjects overall, will be treated in this study. The entire study is expected to last approximately 7 years, with the addition of the expansion cohort and overall survival (OS) follow up.

Cohorts

Phase 1: an open-label escalation cohort of 6 subjects with AML to assess the safety and tolerability of ulocuplumab.

Phase 2: an exploratory, non-comparative open-label expansion cohort of up to approximately an additional 120 AML subjects, randomized in a 1:1:1 manner to the following treatment arms:

- 1) ulocuplumab 800 mg in combination with LDAC 20 mg BID;
- 2) ulocuplumab 1000 mg in combination with LDAC 20 mg BID;
- 3) LDAC 20 mg BID alone.

Randomization will be suspended in the ulocuplumab 1000 mg + LDAC arm while safety data from the first 6 subjects in this arm are evaluated for DLTs (as part of DMC Interim #1). DLTs and all other toxicities are defined and evaluated using the National Cancer Institute Common Terminology Criteria for Adverse Events Version 4.03 (NCI CTCAE v4.03). DLTs are defined based upon events considered to be related to ulocuplumab in combination with LDAC and that occurred during the first cycle of drug administration (28 days). Randomization to the

ulocuplumab 1000 mg + LDAC arm will resume if $\leq 33\%$ of subjects experience a DLT. If $> 33\%$ of subjects are observed with DLTs, this treatment arm will not accrue additional subjects.

[figure not shown]
Study Periods

The study consists of the following 3 periods:

- Screening: the 28 days following initiation of screening assessments and before administration of the first dose of any study drug, during which subjects are evaluated for study eligibility.
- Treatment: subjects will receive LDAC on Days 1-10 of each 28-day cycle. In addition, subjects randomized to arms 1 and 2 will be administered ulocuplumab on Days 1 and 15 (also on Day 8, in cycles 1-2). Subjects who are tolerating study treatment, clinically stable and not progressing rapidly at the end of each cycle may continue with additional cycles until disease progression, development of unacceptable toxicity, intercurrent illness preventing treatment, or patient request or investigator decision to stop treatment. Delay of subsequent cycles for recovery from myelosuppression (or other AE) is allowed at investigator discretion.

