2.4 Blinding and Unblinding

The study is open-label.

Unblinded reports of interim data will be available to the DMC, without the use of fully- or partially-blinded treatment codes. Treatment codes will be provided by the BMS randomization coordinator to the reporting statistician after the database lock for the DMC analyses. Interim results for this exploratory study (for which there will be no inferential testing between treatment groups) will be available for review by a limited number of BMS personnel for planning purposes. Protocol Amendments

There are currently 7 amendments. The history of protocol amendments is summarized in the table below.

Table 2: Protocol Amendments

Amendment	Date	Main changes
1	24 Oct 2014	Clarifications in response to the PMDA review for Clinical Trial Notification
2	7 May 2015	Removal of restriction on AML (newly diagnosed, elderly); modification of prior therapy-related criteria and hepatitis B and C infection criteria
3	2 Nov 2016	Addition of randomized expansion cohort, with primary objective to assess preliminary efficacy; clarification of Phase 2 secondary objectives (safety and tolerability, overall remission [OR], CR/CRi, duration of remission [DoR], OS); added exploratory objectives (receptor occupancy [RO] and biomarkers)
4 (Brazil only)	19 Jan 2017	Clarification of post-study access to therapy in Brazil
5	10 Feb 2017	Addition of central laboratory cytogenetic testing; clarification of dosing and study assessment details
6	29 Mar 2017	Clarification of Phase 2 design (as exploratory, non-comparative; primary analysis to be conducted after all patients had opportunity for 6 months of follow-up; clarified that DoR will be censored on the date of last relapse-related assessment prior to the initiation of alternative anti-cancer therapy); increased local laboratory window allowances for hematology, chemistry and urinalysis to 72 hours; clarification of dose modifications and dose delays; clarification of study design; addition of whole exome sequencing to bone marrow and peripheral blood biomarker testing; added ECG, biomarker, cytogenetic and molecular analysis sections.
7	27 Jul 2017	Revision of exclusion criteria to specify allogeneic transplants in patients who received prior hematopoietic stem cell transplantation; clarification of hematology sampling schedule during cycles 1 and 2; revision of peripheral

		blood and serum/plasma collection criteria during end-of-study treatment and follow-up assessments.

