4.1 Efficacy Endpoints

4.1.1 Primary Endpoint

- Rate of complete remission (CR/CRi), prior to the initiation of any alternative therapy (including any subsequent ulocuplumab 800 mg for subjects in the LDAC alone arm). Response will be assessed by the investigator in accordance with the 2003 International Working Group (IWG) response criteria. The primary analysis will be conducted after all patients have had opportunity for 6 months of follow-up.

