7.5 Efficacy

7.5.1 Complete Remission Rate and Other Response Endpoints

The rate of subjects with complete remission (CR/CRi) will be summarized by a binomial response rate, and corresponding two-sided 95% exact CI using the Clopper and Pearson method. This will be based on best overall response prior to the initiation of any alternative therapy (including any subsequent ulocuplumab 800 mg for subjects in the LDAC alone arm). The rate will be based on all randomized subjects, except at DMC Interim #2, when the calculation will be based on response-evaluable subjects. The rate of OR (= CR/CRi/PR) will similarly be summarized.

- Best response and remission rates summary (best response categorization [CR, CRi, PR, TF]; rates of complete and overall remission)
- Best response listing (with overall response by visit, best response)
- Bone marrow blast assessments plot (% change from baseline)
- Bone marrow blast assessments listing (with bone marrow blast [%], % change from baseline, best reduction, presentation of Auer rods by visit)
- Extramedullary disease listing (disease presence and disease site)
- RBC transfusion listing (type of transfusion)

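### Appendix 1 leaves a leukemia-free marrow with ANC of exactly 1000/µL and recovered platelets outside both CR and CRi; secondarily, no comparison of the investigator's response call with the recorded values is planned

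*Protocol*

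**What the plan says.** Protocol 8.3.1 defines the Phase 2 primary endpoint as the rate of CR or CRi before any alternative therapy, and assigns the judgement to the site: "Investigator will assess best overall response". SAP 4.1.1 agrees: "Response will be assessed by the investigator in accordance with the 2003 International Working Group (IWG) response criteria". SAP 2.4 confirms that "The study is open-label", and SAP 2.2 describes Phase 2 as "an exploratory, non-comparative open-label expansion cohort".

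Protocol Appendix 1 gives the limits. For CR, the peripheral blood line reads "Absolute neutrophil count > 1000" per µL, with platelets of at least 100,000/µL and no blasts. CRi is introduced as "Same criteria as CR except" for platelets below 100,000/µL and/or ANC below 1000/µL.

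On documentation, Appendix 1 says "Local laboratory reports supporting assessments will be sent to BMS", and subjects without such reports are recorded as not done. SAP 7.5.1 plans a summary of best response and remission rates, a "Best response listing (with overall response by visit, best response"), and listings of marrow blasts with Auer rods, extramedullary disease and RBC transfusions.

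**The concern.** Both ANC limits are strict inequalities on the same number, so the value 1000 belongs to neither side. The platelet limits do not have this fault: one is at least 100,000 and the other is below 100,000. The gap lies in the definition of the primary endpoint, and it can place a subject whose marrow has cleared among the non-responders.

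The second issue is who applies the criteria and how that is checked. The assessor knows the arm. In the LDAC alone arm the same judgement decides whether ulocuplumab may be added: Protocol 3.1 allows this when there is no CR/CRi after 4 cycles, or at relapse. A borderline call therefore has a consequence in that arm that it does not have in the combination arms, so any error could differ by arm. Neither document plans a table or sensitivity analysis that sets the call against the values recorded for the same subject.

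**Working it through.** **1. The plan's own precision figures.** Inputs: n = 40 per arm and rates of 0.60 and 0.45 (Protocol 8.1, SAP 5), with two-sided 95% Clopper-Pearson limits (Protocol 8.4.2, SAP 7.5.1). For x responders, the lower limit is the 0.025 quantile of Beta(x, n − x + 1) and the upper limit is the 0.975 quantile of Beta(x + 1, n − x).

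- x = 24: 0.433 to 0.751 (plan: 0.43 to 0.75).
- x = 18: 0.293 to 0.615 (plan: 0.29 to 0.62).

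Both are reproduced and are not in dispute.

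**2. The CR and CRi limits as logical rules.** All other CR criteria are taken as met. CRi is shown under two readings, because the text does not say whether the CR limit for ANC still applies when low platelets are the reason for CRi.

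| ANC (/µL) | Platelets (/µL) | CR | CRi, low platelets alone suffice | CRi, CR limit for ANC still applies |
|---|---|---|---|---|
| 990 | 99,000 | no | yes | yes |
| 990 | 100,000 | no | yes | yes |
| 990 | 101,000 | no | yes | yes |
| 1000 | 99,000 | no | yes | no |
| 1000 | 100,000 | no | no | no |
| 1000 | 101,000 | no | no | no |
| 1010 | 99,000 | no | yes | yes |
| 1010 | 100,000 | yes | no | no |
| 1010 | 101,000 | yes | no | no |

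Every combination with ANC 990 or 1010 falls in exactly one category. ANC 1000 with platelets of at least 100,000 falls in none. ANC 1000 with lower platelets depends on the reading.

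**3. Where the unassigned subject goes.** PR needs 5% to 25% marrow blasts, or fewer than 5% with Auer rods. A marrow with fewer than 5% blasts and no Auer rods satisfies neither. SAP 7.5.1 offers four best-response categories (CR, CRi, PR, TF), so only treatment failure remains. The final SAP 7.5.1 rate is taken over all randomized subjects, so this subject stays in the denominator and leaves the numerator.

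**4. Which recorded values can move the primary rate.** The endpoint counts CR and CRi together.

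- Low ANC or low platelets turn a CR into a CRi, and the numerator is unchanged. Apart from the boundary at 1000, the two counts cannot take a subject out of CR/CRi.
- Marrow blasts, Auer rods, peripheral blasts, extramedullary disease and RBC transfusion dependence can, because they apply to both CR and CRi.

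**5. Effect of one contradicted call.** 1/40 = 0.025, or 2.5 percentage points. From 24/40, one fewer gives 23/40 = 0.575 (0.409 to 0.730). From 18/40, one fewer gives 17/40 = 0.425 (0.270 to 0.591).

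**The case against.** The strongest reply on the gap is that it will hardly ever matter. It needs ANC of exactly 1000, recovered platelets and a clear marrow. Response is assessed every cycle and the best is taken, so the subject must also fail to qualify at every other assessment before alternative therapy. The documents do not give the precision to which ANC is reported, so the frequency cannot be estimated. This stands as a limit on the size of the effect, but it does not make the rule correct.

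On verification, a reader might infer that the primary endpoint goes unchecked. The documents do not support that. Supporting laboratory reports go to the sponsor, missing reports lead to a response of not done, and monitors compare study records with source documents (Protocol 9.1.2). That section also lets a CRF page be the source for the investigator's efficacy assessment, so such a comparison need not test the call against the counts. What is missing is narrower: a planned comparison of call and data. SAP 7.1 and 9 defer output details to a data presentation plan that is not among the documents.

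A reader might also infer that calls unsupported by ANC or platelets would shift the rate by several points. Step 4 of the working shows that they would not.

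Nor could a program replace the investigator. Normal maturation is required for CR but is not among the marrow variables listed in SAP 7.5.1. Extramedullary testing is done only if clinically indicated. Independence from RBC transfusion has no stated time window. Response-related blood tests have flexible timing (Protocol Table 5.1-2), and differentials may be reported as percentages (Protocol 5.3.2). A derived check would also reuse the local marrow readings, so it tests how the criteria were applied, not the readings themselves.

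Finally, Phase 2 has no hypothesis test, so no error rate is at stake. That is true, but the CR/CRi rate is still the primary result.

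**Conclusion.** The gap in Appendix 1 is a definite error in the primary endpoint's criteria as printed. It is certain when platelets are at least 100,000/µL, and depends on the reading when they are lower. Its effect is 2.5 points per affected subject in an arm of 40, and few subjects are likely to be affected. Assigning 1000 to either category gives the same CR/CRi count whenever platelets have recovered, so the repair favours no arm.

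The lack of a planned comparison between the unblinded call and the recorded values is a secondary, supportive point. Its size is unknown: 2.5 points per contradicted call is arithmetic, but the number of such calls is not in the documents. The possibility of a difference between arms rests on the link between the call and add-on ulocuplumab; the documents contain no evidence that bias occurs.

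**What to change.** **Correct.** In Protocol Appendix 1, change one inequality so that ANC of exactly 1000/µL falls in either CR or CRi, and state whether low platelets alone suffice for CRi. Refer to the same wording in SAP 4.1.1. This is a change of text only; sample size and planned precision are unaffected.

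**Consider, as supportive.** In SAP 7.5.1, keep the investigator's call as primary and add:

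- a by-arm concordance table of the call against the recorded values;
- a supportive CR/CRi rate that flags calls contradicted by recorded marrow blasts, Auer rods, peripheral blasts, extramedullary disease or RBC transfusion.

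The SAP would have to set the windows that match blood counts and transfusions to the marrow date, and rules for missing items. It should say that the check is partial, since normal maturation is not listed and extramedullary disease is not tested in everyone. The cost is that specification and programming; no new procedures, samples or readers are needed.

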8.3.2 Secondary Endpoint(s)

- Phase 1 (escalation cohort): Investigator assessed best overall response prior to the initiation of any alternative therapy. Please refer to Appendix 1 for AML response criteria.
- Phase 2 (expansion cohort): Safety and tolerability will be assessed through AEs, AEs leading to discontinuation, SAEs, deaths and laboratory abnormalities in combination therapy during the Treatment period plus 30 days of follow-up will be the primary endpoints for this study. AEs will be graded according to NCI CTCAE v4.03.
- ADA positive for ulocuplumab.
- PK parameters will be determined for subjects in both escalation and expansion cohorts, whenever data permit:

C_{max} Maximum observed serum concentration

C_{trough} Trough observed serum concentration

T_{max} Time of maximum observed ulocuplumab serum concentration

AUC(0-T) Area under the ulocuplumab concentration-time curve from time zero to the last quantifiable concentration (calculated by log- and linear-trapezoidal summation)

AUC(TAU) Area under the ulocuplumab concentration-time curve in one dosing interval

AUC(INF) Area under the ulocuplumab concentration-time curve from time zero to infinity (calculated by summing AUC(0-T) and the extrapolated area, computed by the quotient C_{last}/λ_z)

T-HALF Elimination half-life, determined as $0.693/\lambda_z$

CLT Total body clearance of ulocuplumab (calculated by dividing the total dose of ulocuplumab by its corresponding AUC(INF) value)

V_{ss} Volume of distribution at steady state

AUC from the time of dosing extrapolated to infinity (AUC(INF)) after first dosing and T-HALF will be calculated when feasible. Individual subject PK parameter values will be

derived by non-compartmental methods by a validated PK analysis program. Actual times will be used for the analyses.

- In Phase 2 (expansion cohort): To assess rates of Overall Remission (OR=PR+CR +CRi) as well as duration of complete remission (CR/ CRi) in subjects treated with ulocuplumab at two different dose levels 800 mg and 1000 mg in combination with LDAC.
- In Phase 2 (expansion cohort): To assess efficacy (in terms of rates of CR/CRi and OR and duration of remission, respectively, in subjects treated with LDAC alone, to compare with historical controls of LDAC in the same patient population. Overall survival will also be assessed in this group.
- Duration of remission (DoR) is defined as the time from the date of first documented CR or CRi to the date of death or relapse. For subjects who remain alive and have not relapsed following remission, DoR will be censored on the date of last relapse-related assessment prior to the initiation of alternative anti-cancer therapy.
- The primary ECG endpoint is Δ QTcF, the change from baseline in QTcF, the QT interval normalized using Fridericia's heart rate correction. Other endpoints include QTcF, QT, QRS, PR, HR (heart rate), and QTcB as well as Δ QT, Δ QRS, Δ PR, Δ HR (heart rate), Δ QTcB, the associated changes from baseline. (Note: QTcB is the QT interval normalized using Bazett's heart rate correction.) The schedule for ECGs is given in [Table 5.5.1-1](#) (PK, RO, ADA, and ECG Sampling).
- Overall survival (OS) will also be summarized. OS is defined as the time between the first date of treatment and the date of death due to any cause. A subject who has not died will be censored at the last known alive date.

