4.6 Selection and Timing of Dose for Each Subject

Subjects were/will be assigned to a dose cohort in the order they enter the study.

Subjects in the escalation cohort received ulocuplumab at 600 or 800 mg administered as a single IV infusion on Day 1, 8 and 15 and LDAC at 20 mg BID (40 mg/day) subcutaneously administered on Day 1 - 10 in Cycle 1 (DLT evaluation period) and Cycle 2. Subjects then received ulocuplumab at 600 or 800 mg on Day 1 and 8 in combination with LDAC at 20 mg BID (40 mg/day) on Day 1 - 10 in Cycle 3 and subsequent cycles. A total of 3 subjects were treated at the dose level of 600 mg. A decision to consider the next higher dose level or the next lower dose level or to stop the enrollment upon judging the current dose to be safe was guided by the number of subjects with DLTs observed during the DLT evaluation period based on the mTPI design (see [Section 3.1.1](#)).

Subjects in the expansion cohort will receive ulocuplumab or LDAC alone. Subjects assigned to ulocuplumab arms will receive ulocuplumab 800 mg or ulocuplumab 1000 mg administered as a single IV infusion on Day 1, 8 and 15 and LDAC at 20 mg BID (40 mg/day) subcutaneously administered on Day 1 - 10 in Cycle 1 and Cycle 2. These subjects will then receive ulocuplumab at 800 mg or 1000 mg on Day 1 and 8 in combination with LDAC at 20 mg BID (40 mg/day) on Day 1 - 10 in Cycle 3 and subsequent cycles.

Subjects assigned to the LDAC alone arm will receive 20 mg BID (40 mg/day) on Day 1-10 in every cycle. If ulocuplumab is added to the LDAC alone arm after Cycle 4, the treatment schedule is LDAC 20 mg BID from Day 1 to 10 of each cycle and ulocuplumab 800 mg on day 1, 8 and 15 for the first 2 cycles then ulocuplumab 800 mg on Day 1 and 8 for subsequent cycles. Follow Treatment Procedural Outline ([Table 5.1-2](#)).

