Serum sample for immunogenicity													Applies to Uloocuplumab/LDAC combination arms only See Table 5.5.1-1 and Table 5.5.1-2
Efficacy Assessments													
Leukemia response assessment											X	X	Leukemia response assessment will be evaluated for each cycle using the AML IWG 2003. The results of the response assessments must be reviewed and documented before the first dose of the next cycle.

Table 5.1-2: Treatment Procedural Outline (CA212016)

Procedure ^a	Treatment (28 days/cycle)										EOT ^b	Notes	
	Cycle 1-2 ^c						Cycle 3 and subsequent cycles ^c						All Cycles
	D1 ^d 2-7	D 8 ^e 9-10	D 9-10	D 15 ^{e,f}	D1 ^d 2-7	D 8 ^{g,h}	D 9-10	D 24-28 ⁱ					
Bone marrow aspirate/biopsy											X	The results of the local lab bone marrow aspirate (or biopsy) done as part of routine care will be sent to BMS. Bone marrow aspirate is sufficient for the leukemia response evaluation. The marrow must be of adequate recovery and cellularity for evaluation. If the bone marrow has not yet recovered, repeat the bone marrow until a leukemia response can be determined. The next cycle of treatment is delayed until the marrow is of adequate recovery and cellularity for a response assessment to be completed.	
Diagnostic testing for extramedullary disease											X	Testing for extramedullary disease as part of subject's routine care, if clinically indicated.	
RBC transfusion requirements	X	X		X				X				The threshold for transfusion will be determined at the investigator's discretion.	

Table 5.1-2: Treatment Procedural Outline (CA212016)

Procedure ^a	Treatment (28 days/cycle)										EOT ^b	Notes	
	Cycle 1-2 ^c					Cycle 3 and subsequent cycles ^c							All Cycles
	D1 ^d	D 2-7	D 8 ^e	D 9-10	D 15 ^{e,f}	D1 ^d	D 2-7	D 8 ^{g,h}	D 9-10	D 24-28 ⁱ			

Table 5.1-2: Treatment Procedural Outline (CA212016)

Procedure ^a	Treatment (28 days/cycle)										EOT ^b	Notes	
	Cycle 1-2 ^c						Cycle 3 and subsequent cycles ^c						All Cycles
	D1 ^d 2-7	D 8 ^e 9-10	D 9-10	D 15 ^{e,f}	D1 ^d 2-7	D 2-7	D8 ^{g,h}	D 9-10	D 24-28 ⁱ				
Clinical Drug Supplies													
Ulocuplumab infusion	X	X	X	X	X	X	X	X	X	X			If a subject experiences a Grade 2 infusion reaction with ulocuplumab, the subject will be required to receive prophylactic premedications for subsequent infusions of ulocuplumab. The pre-medications include, but not limited to, diphenhydramine, acetaminophen, and low-dose corticosteroids. See Sections 4.4 and 4.6.

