4.1.2 Secondary Endpoints

- Rate of OR (= PR + CR + CRi)
- DoR: the time from the date of first documented CR/CRi to the date of death or relapse. For subjects who remain alive and have not relapsed following remission, DoR will be censored on the date of last relapse-related assessment prior to the initiation of alternative anti-cancer therapy.
- OS: the time between the first date of treatment and the date of death due to any cause. A subject who has not died will be censored at the last known alive date.

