6.2 Treatment Regimens

Unless otherwise specified, analyses will be performed by Phase 2 treatment arm:

- 1) ulocuplumab 800 mg in combination with LDAC 20 mg BID;
- 2) ulocuplumab 1000 mg in combination with LDAC 20 mg BID;
- 3) LDAC 20 mg BID alone.

Demographic and baseline characteristics, as well as (Phase 2) efficacy, will be summarized (in all randomized subjects) by treatment arm as randomized (per IWRS). Safety and exposure will be summarized (in all treated subjects) by treatment arm as treated. (In general, 'as treated' will be the same as 'as randomized'. However, if a subject received an incorrect drug for the entire period of treatment, the subject will be summarized according to the incorrect drug that the subject actually received.)

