7.5.3 Duration of Remission

For subjects who achieve CR or CRi, DoR will be estimated in the same way as OS.

- KM plot of DoR

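### In the LDAC-alone arm, duration of remission has no add-on limit at its start, so it can include remissions that the CR/CRi rate leaves out

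*Protocol*

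**What the plan says.** **Rates.** Protocol 8.3.1 bases the CR/CRi rate on remission "prior to the initiation of any alternative therapy (including any subsequent ulocuplumab 800 mg for subjects in the LDAC alone arm"). SAP 7.5.1 repeats the limit: "This will be based on best overall response prior to the initiation of any alternative therapy", followed by the same parenthesis about added ulocuplumab. Protocol 8.4.2 and SAP 7.5.1 summarise the overall remission rate in the same way.

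**Duration of remission.** Protocol 8.3.2 defines DoR as "the time from the date of first documented CR or CRi to the date of death or relapse". SAP 4.1.2 gives the same definition. For subjects still alive and without relapse, "DoR will be censored on the date of last relapse-related assessment prior to the initiation of alternative anti-cancer therapy". The parenthesis about added ulocuplumab appears in neither place. SAP 7.5.3 sets the analysis population: "For subjects who achieve CR or CRi, DoR will be estimated in the same way as OS".

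**Arm.** Under SAP 6.2, Phase 2 efficacy "will be summarized (in all randomized subjects) by treatment arm as randomized (per IWRS").

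**Add-on and later assessments.** Protocol 3.1 and 4.4 let an LDAC-alone subject add ulocuplumab 800 mg in two situations: no CR/CRi after four cycles, or relapse after remission. For these subjects Protocol 4.6 says "Follow Treatment Procedural Outline", meaning Table 5.1-2, and that table states: "Leukemia response assessment will be evaluated for each cycle using the AML IWG 2003".

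**Purpose.** Protocol 8.3.2 and SAP 3.2 name CR/CRi, overall remission and DoR in the LDAC-alone arm as the measures to set against historical LDAC results.

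**The concern.** The rate and the duration for one arm should describe the same remissions. Here the rate stops counting at the add-on and the duration does not. A subject who fails four cycles of LDAC, adds ulocuplumab and then remits is a non-responder in the LDAC-alone rate, yet contributes a duration to the LDAC-alone Kaplan-Meier curve. That remission was reached on the combination.

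At stake is the historical comparison. The LDAC-alone DoR curve could mix remissions on LDAC with remissions on ulocuplumab plus LDAC, and its N need not match the CR/CRi count reported for the same arm. The censoring clause does not repair this, because it acts on the end of the interval and not on its start.

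**Working it through.** **1. The plan's own figures.** The documents give no figure for DoR. The nearest planning figure is the exact 95% interval for the CR/CRi rate with 40 per arm (Protocol 8.1, SAP 5). Clopper-Pearson limits are 0.433 to 0.751 for 24/40 and 0.293 to 0.615 for 18/40. They match the stated 0.43 to 0.75 and 0.29 to 0.62 after rounding. The DoR point does not depend on them.

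**2. The rules side by side.**

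| | CR/CRi and OR rates | DoR |
|---|---|---|
| Which remissions count | Only those before alternative therapy | Any first documented CR/CRi |
| Added ulocuplumab named? | Yes | No |
| Arm | As randomized | As randomized |
| Cut at alternative therapy | On the response itself | Only on the censoring date, and only if alive without relapse |

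**3. Which LDAC-alone subjects are affected.**
- Never adds ulocuplumab: not affected by the add-on.
- Remits on LDAC, relapses, then adds ulocuplumab: not affected, because both the start and the event precede the add-on.
- No CR/CRi after four cycles, adds ulocuplumab, never remits: in neither the numerator nor the DoR set.
- No CR/CRi after four cycles, adds ulocuplumab, then remits: outside the numerator, inside the DoR set. This is the only affected group.

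**4. What the censoring clause does to that group.** Inputs: 28-day cycles (Protocol 3.1); add-on after Cycle 4 (Protocol 4.6); response assessment on Day 24 to 28, before Day 1 of the next cycle (Table 5.1-2 and its footnote i). Study day = (cycle − 1) × 28 + day in cycle, assuming no delays.
- Last assessment before the add-on, Cycle 4 Day 24 to 28: 84 + 24 = 108 to 84 + 28 = 112.
- Add-on start, Cycle 5 Day 1: 112 + 1 = 113.
- First assessment after the add-on, Cycle 5 Day 24 to 28: 112 + 24 = 136 to 112 + 28 = 140.
- Second, Cycle 6 Day 24 to 28: 140 + 24 = 164 to 140 + 28 = 168.

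If the add-on counts as alternative anti-cancer therapy and the subject is alive without relapse, DoR = censoring day − start day:
- remission at the end of the first add-on cycle: 112 − 136 = −24 to 108 − 140 = −32 days;
- at the end of the second: 112 − 164 = −52 to 108 − 168 = −60 days.

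If the subject relapses or dies, that is an event and the duration is positive, with no cut. If the add-on does not count, there is no negative time, but remission time on ulocuplumab enters the LDAC-alone curve in full.

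Days 136 to 168 lie inside six months (about 183 days), so without delays such remissions can be present at the final analysis.

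**5. How many.** With R remissions counted in the rate and L first reached after the add-on, the late share of the DoR set is L / (R + L). The documents give neither the number of switchers nor their remission rate, so L may be 0. Purely as an illustration, assume 40 subjects, an LDAC CR/CRi rate of 10% to 30%, 25% to 75% of non-remitters adding ulocuplumab, and 10% to 30% of those remitting:
- low end: R = 40 × 0.30 = 12; L = 40 × 0.70 × 0.25 × 0.10 = 0.7; share 0.7 / 12.7 = 6%;
- high end: R = 40 × 0.10 = 4; L = 40 × 0.90 × 0.75 × 0.30 = 8.1; share 8.1 / 12.1 = 67%.

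None of these input rates is in the documents. The width of the range shows only that the size cannot be settled from the plan.

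**The case against.** The strongest reply is that the intended reading is clear enough. SAP 7.5.3 follows directly on 7.5.1, where remission is judged before alternative therapy. The objective speaks of subjects treated with LDAC alone. Amendment 6 clarified DoR censoring, which suggests that the sponsor wanted DoR kept clear of later treatment. On this view the DoR set is simply the set of counted remissions, and a negative time would tell the programmer that the literal reading is wrong. The detail may also be settled in the Data Presentation Plan, which is not available here. Most of this is fair as a guess at intent, but neither DoR definition nor the analysis section says it. The primary endpoint shows that the authors wrote the limit out where they wanted it.

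It is also true that delays would make late remissions rarer by six months, that responses are listed by visit so late ones could be traced, and that DoR is a descriptive secondary endpoint in an exploratory, non-comparative cohort with no hypothesis test. These points limit the weight of the finding without removing it.

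Three stronger readings go too far:
- A reader might infer that the censoring date always precedes the remission. It does so only under the two conditions in the working.
- A reader might infer that the DoR clause contradicts the primary endpoint. The two use slightly different terms and define different quantities, so this is an ambiguity.
- A reader might infer a bias of known size or direction in the LDAC-alone median. That would need switch rates, remission rates and durations that the documents do not give.

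**Conclusion.** The point holds. As written, the DoR start and analysis set lack the limit that governs the CR/CRi and overall remission rates. A first remission reached after added ulocuplumab would be reported in the LDAC-alone DoR curve without being in that arm's CR/CRi numerator. Both readings of the censoring clause leave a defect: a negative time for ongoing remissions, or remission time on ulocuplumab counted in full.

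The effect is confined to LDAC-alone subjects who switch without prior CR/CRi and then remit. The day counts assume the nominal schedule without delays. The importance is low to moderate: the endpoint is descriptive, but it is one of the measures named for the historical comparison, and the stated rule produces the wrong analysis set for that purpose.

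**What to change.** In Protocol 8.3.2 and SAP 4.1.2 and 7.5.3, limit DoR to subjects whose first CR/CRi was documented before any alternative therapy, and carry over the parenthesis on added ulocuplumab from Protocol 8.3.1. The DoR N then equals the CR/CRi numerator in every arm, which gives a simple programming check. List remissions first reached after the add-on separately, outside the LDAC-alone curve.

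Repeating the parenthesis in the censoring clause is optional and for consistency only. Once the start is limited, a subject following the protocol who remitted on LDAC can add ulocuplumab only after relapse, when the event has already occurred.

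The cost is one clause in each place and one extra listing, with no new data and no change to the primary analysis. The LDAC-alone DoR curve may rest on fewer remissions.
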